4.2.1.2 Reimbursement

4.2.1.2.1 Reimbursement for Aim 1 (intervention study)

Participants will receive \$25 for completing pre- and post-intervention assessments (total=\$50 per couple). Compensation will be provided in the form of gift cards. Gift cards will be mailed to participants once both members of the couple have completed either the baseline or the post-treatment online survey. Once the study team members have

verified that the couple has completed the appropriate surveys, a member of the study team will call the participants to confirm that they have received the gift card and the study team member will document this in our research files.

4.2.1.2.2 Reimbursement for Aim 2 (developmental surveys)

Study-eligible patients who refuse the intervention study but complete brief exploratory surveys (“intervention refusers”) will receive \$10 for participation, also in the form of gift cards. Patients will either receive these in person or will be mailed them, if the survey takes place over the telephone. Regardless of the method of reimbursement, a research team member will confirm receipt of the compensation and will document this in our research files.

4.3. Inclusion and Exclusion Criteria

Overall, eligible patients for this study will be adult (≥ 21 years) partnered breast cancer patients who have completed active treatment for Stage I-III non-recurrent breast cancer between 6 months and 5 years prior who report sexual concerns (see Table 2). Patients’ spouses or partners must also be ≥ 21 years old.

Table 2. Inclusion Criteria

 • Female • Age ≥ 21 years • Has diagnosis of non-recurrent stage I-III breast cancer • Completed active treatment (e.g., chemotherapy, radiation therapy, surgery) 6 months-5 years ago (current use of endocrine therapy is acceptable) • Is currently in a partnered relationship that could involve sexual activity (as determined by eligibility screening script) • Has a partner or spouse who is ≥ 21 • Lives with a romantic partner ≥ 6 months • Score of ≥ 3 on Patient Care Monitor Sexual Concerns screening item⁴⁶ • No hearing impairment in patient or partner
Exclusion Criteria

 • Not able to speak English, as stated in medical record or as observed by study team member • ECOG Performance score > 2 OR too ill to participate as judged by physician/in medical record • Overt cognitive dysfunction or psychiatric disturbance such as suicidal ideation or severe mental illness, as observed or judged by the researcher, referring source, or other qualified observer. • Past history of any cancer other than non-melanoma skin cancer • Currently participating in couple/marital therapy • Currently pregnant

Because male breast cancer patients may experience unique sexuality concerns, we will recruit only female breast cancer patients for the study patient sample. There are no exclusions based on race or ethnicity and every effort will be made to include a diverse patient sample for the current study. Patients are excluded if they are currently participating in couple or marital therapy to avoid confounding improvement in the IE intervention with improvement in co-occurring therapy. Further, we also exclude patients with past history of breast or gynecological cancer, as such patients may have prior sexual complaints and have different needs. Similarly, those with another concurrent cancer treatment are excluded. Pregnant patients are also excluded because they may have different sexual function and sexual concerns. Patients with a hearing impairment are excluded due to the nature of this intervention as occurring over the telephone and therefore requiring active listening. Non-English speakers are similarly excluded. Finally, patients who are too ill, as determined through an ECOG score, medical record, or provider, are excluded because participants are asked to engage in behavioral exercises between intervention sessions and patients who are too ill may not be able to participate fully in such study activities. Finally, because we are collecting outcome data on patients’ psychological distress and well-being,

and because cognitive dysfunction and psychiatric illness could interfere with study activities, patients with overt cognitive dysfunction and psychiatric disturbance are excluded, as described below in Table 2.

Participants in Aim 2 completing the developmental surveys are patients who meet eligibility criteria for the pilot trial (Aim 2) but opt not to participate in the trial. This may be because they do not have time or interest in participating in the full trial, and the developmental survey study allows them the opportunity to contribute to these research efforts despite lack of availability for the pilot study.

No exclusions will be made for any part of the investigation based on sexual orientation, which means that same-sex couples may participate in the pilot trial and those in non-heterosexual relationships may participate in Aim 2.

4.4 Study Data Collection and Measures

4.4.1 Medical Data Collection (Aim 1)

Because patient self-report about medical history can occasionally differ from the data on the same items in patients' charts (e.g., treatments received), we will collect the following data on enrolled patients through medical chart review: date of diagnosis and disease stage, dates and types of treatments and surgeries received for breast cancer, current treatment status, current medication use (including endocrine therapies), and current menopausal status (See Medical Records Data Collection Form in Appendix). The data abstraction will be performed by [name], a Nurse Practitioner and Co-Investigator on our study, or another member of the study team trained or supervised by [name], and entered into our de-identified databases. This medical chart review is documented in the consent form.

4.4.2 Self-Report Data Collection (Aim 1). An overview of study measures and collection time points for participants in Aim 1 (the pilot trial), including number of items in each scale, is in **Table 3**. After consenting, patients and partners will complete pre- and post-intervention outcome measures through a web portal on their home computers using RedCap.

4.4.2.1 Overview of Self-Report Data Collection (Aim 1).

We have given significant thought to the outcome measures included in our study. First, given recent findings from a sexual QOL intervention study suggesting that long survey batteries may contribute to attrition,⁴⁷ attention was given to selecting brief scales or the abbreviated versions of longer scales whenever possible, such as the 7-item Dyadic Adjustment Scale (vs. the 32-item version). These brief scales are psychometrically sound while decreasing the length of time required of participants. Second, the length of the total survey battery is comparable to those administered in many other similar studies, and is shorter than the battery given in our prior pilot studies in colorectal cancer. Computer-based administration of surveys is often less time-consuming for participants than paper and pencil completion⁴⁸ and reduces the need for time spent in mailing back surveys. Finally, nearly all outcome measures chosen are standardized validated comprehensive scales and many are the gold standard for assessing sexual outcomes (e.g., FSFI/IIEF) and other measures have been used successfully by us in our prior studies (see next paragraph for further explanation of these measures).

We will use RedCap to collect data for Aim 1. RedCap is a secure, web-based application that is flexible enough to be used for a wide variety of research studies, offers intuitive interfaces for data entry and real time data validation, and supports easy data manipulation with audit trails and reporting capabilities, including automated export to common statistical packages. RedCap for electronic data collection is preferred over paper and pencil administration for this study because: (1) it can be completed in less time and is therefore potentially less burdensome for participants; (2) it is less burdensome to the investigators in terms of both collection and data entry – essentially eliminating the need for by-hand data entry of self-report measures; (3) it leads to fewer human errors because it obviates the need for by-hand data entry. Participants without computer or internet access will be able to complete data collection through the mail using paper and pencil versions of the electronic data forms, printed out by the couple if possible or sent to the couple

by a study team member. If sent through the mail, surveys will be sent (along with consent forms, if necessary) in separate envelopes with instructions to complete these independently from one another.

In addition to our collection of the measures assessing preliminary efficacy of the IE intervention (described below in 4.4.2.2), we will also collect data on patients’ and partners’ self-efficacy for coping with sexual problems with three items we have used in our recent trial,⁴⁹ and on frequency of patient sexual activities and use of sexual aids assessed with items from the PROMIS Sexual Function measure⁵⁰ to generate effect sizes for the future trial. We also include two items that we developed and assessed in a prior prospective study in colorectal cancer that assess the extent to which sexuality is important to the individual, based on a theoretical model of flexible coping developed by the PI.⁵¹ In addition, we will collect data from both patients and partners on cancer-specific distress,⁵² which has become commonplace in couple-based cancer interventions⁵³ and is important to track given the distress experienced by patients’ spouses in confronting their partners’ cancer diagnoses.⁵⁴ Demographic characteristics (e.g., age, race/ethnicity) will be assessed through self-report. Additionally, both patients and partners will complete a validated self-report version of the Charlson Comorbidity Index,⁵⁵ which will provide a measure of medical illness comorbidity. This is relevant given the relation between medical illnesses (e.g., cancer, diabetes, heart disease) and sexual function. Particularly for men, but also for women, medical comorbidity is a major determinant of sexual dysfunction.⁵⁶

4.4.2.2 Preliminary Efficacy (Aim 1) will be measured through the following measures shown in **Table 3**, all of which have been validated and psychometrically tested in the context of cancer: **patient and partner sexual QOL outcomes** (sexual function, sexual satisfaction, sexual intimacy, sexual distress) and **relationship outcomes** (emotional intimacy, sexual communication, relationship quality), and **patient psychosocial outcomes** (body image distress, psychological distress). These measures are included in the Self-Report Materials in the Appendix.

4.4.2.3 Feasibility (Aim 1) will be measured through study accrual, attrition, and session completion. Participants will also complete a measure of adherence to study recommendations or review of materials taught within sessions in both conditions through the web portal immediately prior to sessions 2-4 (Materials Review Form; See Self-Report Materials in Appendix) that will help us assess the extent to which engagement in study activities was feasible, while also serving as a potential mediator of change. Couples will be instructed to complete these independently using online survey links. This survey is the same for participants in both conditions and thus does not assess intervention-specific skills or information.

4.4.2.4 Acceptability (Aim 1) will be assessed with the post-intervention assessment through the Client Satisfaction Questionnaire-8 item version (CSQ-8),⁵⁷ a validated measure that elicits the client’s perspective on the value of services received. Participants in both conditions will complete the CSQ-8. For comparability with the prior pilot studies, all participants will complete items used in those trials that capture ease of participation, relevance, helpfulness of the intervention, and therapist rapport. In addition, IE participants will be asked about their preferences regarding attending a follow-up “booster” session at the end of the four telephone sessions, which may be implemented in future larger trials using this intervention. Going forward, IE participants will be asked these items as part of the post-treatment assessment. IE participants who have already completed the post-treatment assessment will be contacted by the study team to assess their preferences for a follow-up session. Finally, those assigned to the IE condition will complete items assessing the ease and frequency of use, and helpfulness of skills taught in the intervention (e.g., communication; See Self-Report Materials in Appendix).⁴¹

Table 3. Outcome Measures								
Measure	Construct	# Items	Baseline	Session 1	Session 2	Session 3	Session 4	Post-Treatment
Patient and Partner Sexual QOL Outcomes								
Female Sexual Function Index (FSFI)* ^{58,59}	Sexual function	19/15	X					
International Index of Erectile Function (IIEF) ⁶⁰								

PROMIS Sexual Satisfaction Items ⁶¹	Sexual satisfaction	5	X					X
Female Sexual Distress Scale-Revised* (FSDS-R) ⁶²	Sexual distress	13	X					X
PAIR Sexual Intimacy Subscale ⁶³	Sexual Intimacy	6	X					X
Beliefs (self-efficacy) ^{64,65}	Self-efficacy	3	X					X
Intimate Activities and Use of Sexual Aids (PROMIS Items) ^{27,61*}	Frequency of sexual activity/use of aids	8	X					X
Patient and Partner Relationship Outcomes								
PAIR Emotional Intimacy Scale ⁶³	Emotional Intimacy	6	X					X
Dyadic Sexual Communication Scale (DSCS) ⁶⁶	Sexual communication	13	X					X
Dyadic Adjustment Scale-7 item (DAS-7)	Relationship quality	7	X					X
Patient Psychosocial Outcomes – ONLY COMPLETED BY PATIENT								
Body Image Scale (BIS) ⁶⁷	Body image distress	10	X					X
Patient Health Questionnaire-9 item (PHQ-9) ⁶⁸	Distress (depression)	9	X					X
Generalized Anxiety Disorder 7-item (GAD-7) ⁶⁹	Distress (anxiety)	7	X					X
Additional Items Completed by Patients/Partners								
Baseline demographic information for patient/partner	Demographic data	12/7	X					
Post-treatment demographic items	Demographic data	2						X
Charlson Comorbidity Index ⁵⁵	Medical comorbidity	11	X					
Impact of Events Scale ⁵²	Cancer-Specific Distress	22	X					X
Sexual Self-View (importance of sexuality to self)	Sexual self-view	2	X					X
Total # of items in baseline scales								
Patients	153							
Partners	95							
Intervention Process Forms (completed individually)								
Program Evaluation Form	Credibility	7		X				
Materials Review Form	Adherence	7			X	X	X	
CSQ-8 ⁵⁷	Acceptability	8						X
Additional Acceptability Questions ^{64,65}	Acceptability	18						X
Skills Assessment ^{**64,65}	Utilization of skills	3						X
Additional Information Completed by Patients								
Post-treatment demographic information	Demographic/medical data	2						X
Total # of items in post-treatment scales								
Patients	169							

Partners	118							
* indicates that patients only complete this measure ** indicates that only IE participants complete this measure								

4.4.3 Self-Report Data Collection (Aim 2)

All data collected from participants in Aim 2 (developmental survey study) will be collected using the Developmental Survey (See Developmental Aim Draft Survey in Appendix), which will be administered verbally, rather than by the patients and is thus in an interview style, or over the web. This survey collects information on patients’ reasons for lack of interest in participating, preferences for resources or programs addressing sexual/intimacy concerns, and race/ethnicity. More information about this survey can be found in section 4.7. In addition, if patients endorse the item from the screening script with regard to keeping their information from the screening, we will enter these information (e.g., age, breast cancer data) into our de-identified research files for further descriptive information about this sub-sample.

4.5.1 Overview of Randomization and Intervention Conditions (Aim 1)

Couples will be randomized with an allocation ratio of 2:1 to either the IE or the Educational Control (Living Healthy Together) condition, in order to maximize data generated on the active condition, with stratification by age at diagnosis (≤ 45 vs. > 45) using the age obtained by patients during the screening. Because of the broad intimacy targets of this intervention, outcomes may not differ by menopausal status and therefore we will not stratify by this variable. However, because sexual function can differ by menopausal status, we will investigate menopausal status as a possible moderator of outcome in the intervention group for future research.

Randomization will occur once both members of the couple have consented, completed baseline surveys, and are scheduled for their first intervention session. At this time, the couple will be sent sealed study materials along with the instructions to leave the envelopes sealed until they “meet” with their interventionist for session 1. It is important to keep the study condition a secret from participants until Session 1 to reduce the chances for unequal drop-out prior to Session 1, which could occur if patients/partners are more motivated to attend sessions in one study group as opposed to the other.

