4.2.1.1 Patient Contact and Screening

Study candidates will be recruited (a) over the telephone using a study letter sent after identification of appropriate candidates through providers’ schedules, or after identification through the Fox Chase Cancer Registry, (2) through in-person clinic recruitment, and (3) through advertisements in clinic and patient areas (e.g., education and resource

room). Pre-screening of patients' charts by our recruitment team prior to patient contact helps to ensure that only potentially eligible candidates who meet initial criteria (e.g., age, breast cancer diagnosis and stage, ECOG score, English speaking status) will be contacted regarding participation in the study in order to minimize potential patient burden. The initial contact will be conducted with approval from the treating physician/provider (e.g., NP) and will be from the research team and/or the treating provider. For patients identified through the Registry, lists of potentially eligible candidates will be approved by the patients' physician prior to sending the introductory letter. Potential candidates who have not called to opt out of the study or otherwise opted out will be called by a research member to confirm their eligibility.

For interested candidates, screening will determine eligibility (see Patient Screening Script in Appendix) and will also include a discussion of study procedures, risks, benefits, and the voluntary nature of their participation, and the fact that it will not affect their medical care. Screening the patient for eligibility may occur over the telephone or in person and will include assessment of age, disease status and stage, partner status and age, treatment status and length of time since completing treatment, use of hormone therapy, hearing impairment of patient and partner, current pregnancy, past history of breast or gynecological cancer, current treatment for a concurrent cancer, current participation in marital therapy, and sexual concerns. We are currently using many similar items, including the sexual concerns screening item, in protocol 14-833 and have had success with these screening items. Medical record review will confirm the patients' breast cancer diagnosis, stage, and treatment status, as described in the screening script (or in pre-screening).

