13.1.1. Primary and Secondary Outcome Variables

13.1.1.1. Primary outcomes are feasibility and acceptability of the study. Feasibility will be measured through study accrual, attrition, and session completion. Acceptability is measured using the CSQ-8 (See Self-report Materials in Appendix).

13.1.1.2. Secondary outcomes are preliminary efficacy of the study in patient and partner sexual outcomes (sexual function, sexual satisfaction and intimacy, sexual distress), patient and partner relationship outcomes (emotional intimacy, sexual communication, relationship quality), and patient psychosocial outcomes (body image distress, psychological distress). The measures assessing these outcomes can be found in Table 3 above.

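### Does taking the age stratum from screening undermine stratification by age at diagnosis?

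*Combined protocol and SAP*

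**What the plan says.** Section 4.5.1 of the combined protocol and SAP allocates couples 2:1 "with stratification by age at diagnosis (≤ 45 vs. > 45) using the age obtained by patients during the screening". Age is the only stratification factor. The same section fixes the timing: "Randomization will occur once both members of the couple have consented, completed baseline surveys, and are scheduled for their first intervention session".

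Section 4.2.1.1 describes two earlier steps. Chart pre-screening is meant to ensure that the team contacts "only potentially eligible candidates who meet initial criteria (e.g., age, breast cancer diagnosis and stage, ECOG score, English speaking status"). Screening of the patient then "will include assessment of age, disease status and stage, partner status and age, treatment status and length of time since completing treatment", among other items, and the section refers the reader to a screening script in the appendix.

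Section 4.3 sets the time window through the inclusion criterion "Completed active treatment (e.g., chemotherapy, radiation therapy, surgery) 6 months-5 years ago". Section 4.4.1 adds chart abstraction for enrolled patients, including "date of diagnosis and disease stage". Section 4.4.2.1 collects age again by self-report.

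On analysis, section 13.1.1 makes feasibility and acceptability primary and states that "Secondary outcomes are preliminary efficacy of the study in patient and partner sexual outcomes", followed by relationship and psychosocial outcomes. Section 13.1.2.3 computes a crude between-group effect size from change scores and does not use the stratum.

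**The concern.** The factor is named as age at diagnosis, but its source is an age obtained at screening, and the screening list in section 4.2.1.1 says only age. Section 4.3 phrases eligibility in terms of present age: "eligible patients for this study will be adult (≥ 21 years) partnered breast cancer patients who have completed active treatment". A reader can reasonably suspect that current age will go into the randomisation.

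The two ages differ for every participant. Active treatment ended 6 months to 5 years before, so diagnosis lies further back by the length of treatment. Any error runs one way only: a woman diagnosed at 45 or younger who has since passed 45 would be placed in the older stratum, and never the reverse.

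If that happened, three things would be at stake: some balance on the intended factor, a little precision in the effect sizes meant to inform the larger trial, and the accuracy of the stratum label in the report.

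**Working it through.** **No figure to reproduce.** The plan gives no age distribution, expected stratum sizes, block size or age effect. From the documents come 30 couples, 2:1 allocation (20 and 10), the cut at 45, and 6 months to 5 years since the end of treatment. Everything else below is assumed, and all of it applies only if current age is used.

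**Step 1. How many women change stratum?** Assume age at diagnosis is normal with SD 11, limited to 21 or over, and the gap from diagnosis to screening is uniform on 0.75 to 6 years. A woman changes stratum if she is under 46 at diagnosis and 46 or over at screening. Simulation gives the probability p; the other columns follow.

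| Mean age at diagnosis | p | Expected of 30 = 30p | Chance of at least one = 1 − (1 − p)^30 |
|---|---|---|---|
| 50 | 0.105 | 3.2 | 96% |
| 55 | 0.075 | 2.2 | 90% |
| 60 | 0.043 | 1.3 | 73% |

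A separate simulation took time since treatment as uniform on 0.5 to 5 years and added an assumed treatment length of up to 1.5 years. With mean age 50 to 60 and SD 10 it gives 1.0 to 4.4 of 30. With means of 48 to 60 and SDs of 8 to 12 it gives 0.6 to 5.5. So 1 to 4 is a central range and not a bound.

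**Step 2. Does this bias the comparison?** No. Current age and age at diagnosis are both fixed before the couple is allocated. Allocation is random within whichever strata are formed.

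**Step 3. What does it cost in precision?** With a residual SD of 1, the squared standard error of the difference in mean change is 1/20 + 1/10 = 0.15, plus a term for chance imbalance on the age split. Let D be the difference in change across the cut at 45, in SD units, and s the SD of the between-arm difference in the proportion diagnosed at 45 or younger. Then

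SE = √(0.15 + (D·s)²).

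Take D = 0.5 and simulated s for permuted blocks of 3 (the plan does not state a block method):

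- Mean 50: s = 0.043 with the correct strata and 0.123 with screening-age strata. √(0.15 + 0.0615²) / √(0.15 + 0.0215²) = 1.011, a rise of 1.1%.
- Mean 55: s = 0.048 and 0.112. √(0.15 + 0.056²) / √(0.15 + 0.024²) = 1.008, a rise of 0.8%.
- Mean 60: s = 0.053 and 0.094. √(0.15 + 0.047²) / √(0.15 + 0.0265²) = 1.005, a rise of 0.5%.

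Blocks of 6 give 1.1%, 0.9% and 0.4%. If age acts gradually (0.5 SD per 20 years), the rise is 0.3% to 0.5%. Letting the effect run from 0.3 to 0.8 SD widens the range to 0.15% to 2.8% for a step at 45, and to 0.1% to 1.2% for a gradual effect.

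**Step 4. Set this against the scale of the trial.** The standard error itself is about √0.15 = 0.39 SD. Section 13.1.2.1 treats attrition of about 30% as its limit of feasibility. At that level, with completers only, the arms would be 14 and 7, and the standard error √(1/14 + 1/7) = 0.46, which is 20% larger. An effect of about 1% is lost beside that.

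**Step 5. Would adjusting for the stratum help?** With screening-age strata, D = 0.5 and blocks of 3, the simulated sampling SD of the crude and the stratum-adjusted estimates is 0.3921 and 0.3922 (mean 50), 0.3912 and 0.3920 (mean 55), and 0.3903 and 0.3923 (mean 60). Adjustment buys no precision.

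**The case for a change.** The strongest case for acting is that this is the trial's only stratifier and the remedy would be one sentence. As written, staff could apply either age, or even differ between couples. Under the current-age reading a sizeable share of the benefit of stratifying is lost. On the variance scale, for mean age 50 and blocks of 3, with s = 0.185 for no stratification, the share lost is 1 − (0.185² − 0.123²)/(0.185² − 0.043²) = 41%.

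The ambiguity is real and that part stands. The share lost is correct arithmetic, but it is a share of something small. With D = 0.5, going from the correct strata to none at all raises the standard error by √(0.15 + 0.0925²) / √(0.15 + 0.0215²) − 1 = 2.7%, so losing part of that cannot change how pilot effect sizes are used.

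The current-age reading is also not the better supported one. Within the sentence in section 4.5.1, the age referred to is most naturally the one just named, age at diagnosis, as reported by the patient. The list in section 4.2.1.1 is a summary that defers to the script. Nor is eligibility the only purpose of screening age: section 4.2.1.1 keeps screening data, with permission, to inform future studies, section 4.4.3 keeps them to describe the Aim 2 sample, and section 4.5.1 itself uses the age for stratification.

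**Conclusion.** The concern does not call for a change. Section 4.5.1 leaves out one detail, and the operational document to which the plan defers may well supply it. Even on the unfavourable reading there is no bias, and no primary outcome, test or sample size is touched. The standard error of the secondary effect sizes rises by about 0.3% to 1.1% in the central scenarios, and by at most 2.8% over the age effects tried. A stratum built on current age would still be a valid stratum, correlated with the intended one.

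The labelling risk can be handled with data already planned: date of diagnosis from the chart, together with self-reported age at baseline, gives age at diagnosis to within about a year for descriptive reporting.

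The absence of bias follows from the timing of randomisation and needs no assumption about ages. The sizes rest on assumed age distributions, gaps, permuted blocks and age effects, none of which the documents give, and on all 20 and 10 couples being analysed.
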